## 4.3 Sample Size and Power

With approximately 2000 participants in Cohort A and 2000 participants in Cohort B (a total of 4000) exposed to study vaccine in the mRNA-1083 (40  $\mu$ g) + Placebo group, this study will have approximately over 95% probability to observe at least 1 participant with an AE given a true 0.1% AE rate.

A subset of participants will be randomly selected from the FAS of Cohort A and B, respectively, to be tested by microneutralization assay according to the secondary objective.

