9.3. Sample Size Determination

With a total of 4000 participants for each cohort, approximately 2000 participants in Cohort A and 2000 participants in Cohort B (a total of 4000) will be exposed to study vaccine in the mRNA-1083 (40 μ g) + Placebo group. This will have approximately over 95% probability to observe at least 1 participant with an AE given a true 0.1% AE rate.

A subset of participants will be randomly selected from the FAS of Cohort A and B, respectively, to be tested by microneutralization assay according to the secondary objective (Section 3). Details of the sampling strategy will be documented in the SAP.

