9.5.3. Safety Analyses

The safety analyses will be separately performed by Cohort A and B, respectively.

All safety analyses will be based on the Safety Set of each cohort, except summaries of solicited ARs, which will be based on the Solicited Safety Set of each cohort. All safety analyses will be provided by treatment group. Participants will be included in the treatment group corresponding to what they actually received.

Safety and reactogenicity will be assessed by clinical review of all relevant parameters, including solicited ARs (local and systemic events), unsolicited AEs, SAEs, AESIs, MAAEs, severe AEs, and AEs leading to withdrawal from study participation.

The number and percentage of participants with any solicited local AR, solicited systemic AR, and solicited AR during the 7-day postinjection follow-up will be summarized. A two-sided 95% exact CI using the Clopper-Pearson method will also be provided for the percentage of participants with any solicited AR. Solicited ARs and grades are defined in Section 10.5.

The number and percentage of participants with unsolicited AEs, SAEs, AESIs, MAAEs, severe AEs, and AEs leading to withdrawal from study participation will be summarized. Unsolicited AEs will be coded according to MedDRA and presented by MedDRA system organ class and preferred term.

Solicited ARs will be coded according to the MedDRA for AR terminology. The Toxicity Grading Scale for Healthy Adult and Adolescent Volunteers Enrolled in Preventive Vaccine Clinical Trials (DHHS 2007) will be used in this clinical study.

The number of events of unsolicited AEs, SAEs, AESIs, MAAEs, severe AEs, and AEs leading to withdrawal from study participation will be reported in summarization tables accordingly.

The analysis strategy for safety parameters is presented in Table 10. For all other safety parameters, descriptive summary statistics will be provided. Further details will be described in the SAP.

Table 10: Analysis Strategy for Safety Parameters

Safety Endpoint	Number and Percentage of Participants	Number of Events	95% CI
Any solicited AR (overall and by local, systemic)	✓	NA	✓
Any unsolicited AE	✓	✓	NA
Any unsolicited treatment-related AE	✓	✓	NA
Any SAE	✓	✓	NA
Any treatment-related SAE	✓	✓	NA
Any unsolicited AESI	✓	✓	NA
Any unsolicited treatment-related AESI	✓	✓	NA
Any unsolicited MAAE	✓	✓	NA
Any unsolicited treatment-related MAAE	✓	✓	NA
Any unsolicited severe AE	✓	✓	NA
Any unsolicited treatment-related severe AE	✓	✓	NA

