## 5.6 Safety Set

The Safety Set consists of all participants who are randomly assigned and receive the study intervention. The Safety Set will be used for all analyses of safety, except for the solicited ARs. Participants will be included in the treatment arm corresponding to what they actually received according to the as treated scheme given below in Table 3.

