# 6.5 Safety Analyses

Safety and reactogenicity will be assessed by clinical review of all relevant parameters, including solicited ARs (local and systemic events), unsolicited AEs, SAEs, AESIs, MAAEs, severe AEs, and AEs leading to withdrawal from study participation.

All safety analyses will be provided for the Cohort A and Cohort B substudies separately.

Participants will be included in the treatment arm corresponding to what they actually received and will be based on the Safety Set, except summaries of solicited ARs, which will be based on the Solicited Safety Set, unless otherwise specified. When summarizing the number and percentage of participants with an event, participants will be presented according to the highest severity/toxicity in the summaries by severity/toxicity. Imputation rules for missing/partial dates is detailed in Appendix E.

An additional pooled safety analysis that combines the mRNA-1083 + placebo arm from the two cohorts may also be carried out. Summaries of local solicited ARs and AEs may also be presented by vaccination group and injection content received in the corresponding side/deltoid.

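### Does the stated chance of over 95% of seeing a 0.1% adverse event fail because safety is analysed cohort by cohort?

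*SAP*

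**What the plan says.** SAP section 4.3 gives the safety rationale for the sample size. It counts "approximately 2000 participants in Cohort A and 2000 participants in Cohort B (a total of 4000) exposed to study vaccine" and concludes that the study has "approximately over 95% probability to observe at least 1 participant with an AE given a true 0.1% AE rate". Protocol section 9.3 gives the same 2000 plus 2000 and continues: "This will have approximately over 95% probability to observe at least 1 participant with an AE given a true 0.1% AE rate". In both documents the statement sits in the general part of the section, ahead of the cohort subsections, which deal only with immunogenicity power.

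On analysis, Protocol section 9.5.3 says: "The safety analyses will be separately performed by Cohort A and B, respectively". SAP section 6.5 agrees: "All safety analyses will be provided for the Cohort A and Cohort B substudies separately". The same SAP section adds: "An additional pooled safety analysis that combines the mRNA-1083 + placebo arm from the two cohorts may also be carried out". Protocol section 9.5.3 does not mention pooling. Neither document gives a detection probability for one cohort.

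**The concern.** The sizing statement uses one denominator and the planned analyses use another. Safety is a primary objective in each cohort (Protocol sections 3.1 and 3.2, SAP section 2.1), and the cohorts are described as independent substudies with their own analysis sets. Each safety table therefore rests on about 2000 mRNA-1083 recipients, half the number behind the stated probability. The one analysis that would use all 4000 is optional in the SAP and absent from the protocol.

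If the stated probability really belonged to each substudy, it would be overstated. Someone reading a cohort report with no cases of a rare event might take that as stronger evidence against a 0.1% rate than 2000 recipients can supply.

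**Working it through.** **Inputs**
- True event rate p = 0.001 (SAP section 4.3: "given a true 0.1% AE rate").
- Exposed to mRNA-1083: 2000 per cohort, 4000 in all (Protocol section 9.3, SAP section 4.3).
- No deduction for dropout. SAP section 5.6 counts everyone dosed: "The Safety Set consists of all participants who are randomly assigned and receive the study intervention".

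**Formula.** The probability of at least one case among n recipients is 1 − (1 − p)^n.

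**The plan's own figure**
- n = 4000: 1 − 0.999^4000 = 98.2%. The claim of over 95% is met.
- Even if the 15% dropout assumed for immunogenicity were applied, n = 0.85 × 4000 = 3400 and 1 − 0.999^3400 = 96.7%. The claim is still met.

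**One cohort**
- n = 2000: 1 − 0.999^2000 = 86.5%, so a given cohort shows no case with probability 13.5%.
- Smallest n for 95%: ln(0.05) / ln(0.999) = 2994.2, so 2995. This lies between 2000 and 4000.
- Rate at which 2000 recipients give 95%: 1 − 0.05^(1/2000) = 0.150%, about 1 in 668.

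**Two cohorts tabulated separately**
- Both miss: 0.999^2000 × 0.999^2000 = 0.1352 × 0.1352 = 0.0183, or 1.8%.
- At least one shows a case: 1 − 0.0183 = 98.2%, the same as for the pool.

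The last step settles the point. The stated property is that the study observes at least one affected participant. Both cohorts' safety summaries are planned (Protocol section 9.5.3, SAP section 6.5), as are listings of individual adverse events (SAP section 6.5.2). A case in either cohort will therefore appear in planned output. Pooling adds two counts together. It cannot change whether their sum is zero.

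**Sensitivity to a common rate.** The 98.2% assumes 0.1% in both age groups. If the event occurred at 0.1% in one cohort and never in the other, the chance of any case would be 86.5%, with or without pooling.

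**The case for a change.** The best argument for a change is about consistency. Immunogenicity power is given cohort by cohort, and only the safety statement moves to the combined denominator. Each cohort's primary analysis is triggered by its own Day 29 completion (Protocol sections 9.6.1 and 9.6.2), so one cohort may report first on about 2000 recipients. The SAP also commits to comparing immune responses between the two mRNA-1083 arms (section 6.3.2.3) while leaving the pooled safety summary optional. And rates may differ between age groups, which makes a per-cohort figure informative in its own right. Zero cases in 2000 gives a one-sided 95% upper bound of about 0.15%, against about 0.075% for zero in 4000.

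This is right as far as it goes. The per-cohort figure is missing, and a reader of one cohort's report would be better informed with it. It does not show that the statement is wrong, because the 4000 basis is given alongside the probability in both documents. Nor does it make a case for mandatory pooling. The optional pool covers only the mRNA-1083 arms, so it offers no comparison with control, and it leaves the chance of observing a case unchanged. If the rates differ by age, pooling does not help either: an event confined to one cohort has an 86.5% chance of being seen in both layouts.

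**Conclusion.** The statement stands and no change to the plan follows. It is correct for the study-wide exposure on which it is based (98.2% against a claim of over 95%), and it holds across the two separately reported cohorts without pooling, provided the rate is 0.1% in both and all 4000 are dosed.

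What remains is a figure the documents leave out: 86.5% per cohort at a 0.1% rate, or 95% at about 0.15%. Anyone can derive it in one line from numbers in the same section. The safety analyses are descriptive, with counts and percentages, and confidence intervals for solicited reactions only. No hypothesis, threshold or success criterion uses a detection probability, and neither document sets 95% at 0.1% as a target for each cohort. Adding the figure would alter no analysis or result, and doing so in the protocol would mean an amendment with ethics approval (Protocol section 10.1.1). Making the pooled summary mandatory would only add up counts that are already to be reported. If the section is being edited for another reason, giving the per-cohort figure beside the combined one would be a courtesy to the reader.

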#### 4.3.1 Cohort A Substudy (≥65 Years)

Immunogenicity results from the participants in Cohort A, will contribute to the primary immunogenicity analyses for Cohort A. With approximately 2000 participants (including the assumed approximate 15% drop-outs) receiving mRNA-1083 (40  $\mu$ g) + Placebo, and 2000 receiving Fluzone HD + Spikevax, this will provide at least 95% overall power to demonstrate NI across the five co-primary immunogenicity endpoints for GM level at Day 29 between mRNA-1083 (40  $\mu$ g) + Placebo and Fluzone HD + Spikevax in all the 4 influenza strains and 1 SARS-CoV-2 strain. The power evaluation assumes a 2-sided alpha of 0.025, approximately

15% drop-out rate, true GMR of 0.85 (SD of antibody level in natural logarithm being 1.5) and a NIM of 1.5 for GMR in all the 4 influenza strains and 1 SARS-CoV-2 strain.

The study has at least 95% overall power to demonstrate NI across the five co-primary immunogenicity endpoints for SCR or SRR between mRNA-1083 (40  $\mu$ g) + Placebo and Fluzone HD + Spikevax in all the 4 influenza strains and 1 SARS-CoV-2 strain. The power evaluation assumes a 2-sided alpha of 0.025, approximately 15% drop-out rate, an underlying SRR or SCR of 68% in the mRNA-1083 (40  $\mu$ g) + Placebo group and an SRR or SCR of 70% in Fluzone HD + Spikevax group (with a true SRR or SCR difference being -2%) and a NIM of 10% for the rate difference in the 2 influenza A strains and 1 SARS-CoV-2 strain, and assumes an underlying SCR of 58% in the mRNA-1083 (40  $\mu$ g) + Placebo group and a SCR of 60% in Fluzone HD + Spikevax group (with a true SCR difference being -2%) and a NIM of 10% for the rate difference in the 2 influenza B strains.

#### 4.3.2 Cohort B Substudy (≥50 to <65 Years)

Immunogenicity results from the participants in Cohort B will contribute to the primary immunogenicity analyses for Cohort B. With approximately 2000 participants (including the assumed approximate 15% drop-outs) receiving mRNA-1083 (40  $\mu$ g) + Placebo, and 2000 receiving Fluarix + Spikevax, this will provide at least 95% overall power to demonstrate NI across the five co primary immunogenicity endpoints for GM level at Day 29 between mRNA-1083 (40  $\mu$ g) + Placebo and Fluarix + Spikevax in all the 4 influenza strains and 1 SARS CoV 2 strain. The power evaluation assumes a 2-sided alpha of 0.025, approximately 15% drop out rate, true GMR of 0.85 (SD of antibody level in natural logarithm being 1.5) and a NIM of 1.5 for GMR in all the 4 influenza strains and 1 SARS CoV 2 strain.

The study has at least 95% overall power to demonstrate NI across the five co-primary immunogenicity endpoints for SCR or SRR between mRNA-1083 (40  $\mu$ g) + Placebo and Fluarix + Spikevax in all the 4 influenza strains and 1 SARS-CoV-2 strain. The power evaluation assumes a 2-sided alpha of 0.025, approximately 15% drop-out rate, an underlying SRR or SCR of 68% in the mRNA-1083 (40  $\mu$ g) + Placebo group and an SRR or SCR of 70% in Fluarix + Spikevax group (with a true SRR or SCR difference being 2%) and a NIM of 10% for the rate difference in the 2 influenza A strains and 1 SARS CoV 2 strain, and assumes an underlying SCR of 58% in the mRNA 1083 (40  $\mu$ g) + Placebo group and a SCR of 60% in Fluarix + Spikevax group (with a true SCR difference being 2%) and a NIM of 10% for the rate difference in the 2 influenza B strains.

#### 4.4 Randomization

Randomization will be performed using an interactive response technology (IRT) by a 3rd party vendor.

#### **Cohort A Substudy (≥65 Years)**

In Cohort A randomization (in a 1:1 ratio) will be stratified by age groups (65 to <75 years and  $\geq$ 75 years of age where at least 10% of participants are  $\geq$ 75 years of age) and the influenza vaccine status in the most recent influenza season (received or not received since September 2022).

### **Cohort B Substudy (≥50 to <65 Years)**

In Cohort B randomization (in a 1:1 ratio) will be stratified by the influenza vaccine status in the most recent influenza season (received or not received since September 2022).

## 4.5 Blinding and Unblinding

This is an observer-blind study. An independent unblinded statistical and programming team will perform the preplanned primary analysis (see Section 4.5). Sponsor team members will be prespecified to be unblinded to the primary analysis and will not communicate the results to the blinded investigators, clinic staff, clinical monitors, or participants.

The planned analyses are described in Section 6.7 of this SAP. For further details on preidentified sponsor and CRO team members (identified by role), and the level of unblinding (treatment arm level unblinding and/or participant level unblinding) please refer to the study Data Blinding Plan.

#### 5 ANALYSIS SETS

Each of Cohort A and Cohort B substudies will have its separate set of analysis populations defined as below that will be applied in separate statistical analyses planned in each of the 2 cohorts, respectively.

#### 5.1 Randomization Set

The randomization set consists of all participants who are randomly assigned. Participants will be included in the treatment arm to which they are randomized.

## 5.2 Full Analysis Set

The Full Analysis Set (FAS) consists of all participants who are randomly assigned and receive the study intervention. Participants will be analyzed according to the treatment arm to which they were randomized.

## 5.3 Immunogenicity Set

All participants in the FAS who have baseline and Day 29 antibody assessment via HAI or PsVNA assay. Participants will be analyzed according to the treatment arm to which they were randomized.

## 5.4 Per Protocol Immunogenicity Set

The Per Protocol Immunogenicity Set (PPIS) will be used as the primary analysis set for analyses of immunogenicity in Cohort A or Cohort B unless otherwise specified. Participants will be analyzed according to the treatment arm to which they were randomized.

The PPIS consists of all the participants in the FAS who comply with the timing of immunogenicity blood sample collections to have both Baseline (see Section 6.1) and Day 29 assessments using a window of -7 to +14 days, have no major dosing error, have negative RT-PCR test for influenza and SARS-CoV-2 on Day 1, and have no major protocol deviations or conditions/medications that affect the immune response.

The major dosing error ranges, available in Table 2, will be used to determine participant exclusion from the PPIS analysis populations.

## 5.5 Per Protocol Immunogenicity Set for MN assay

The PPIS for MN assay will be used as the secondary analysis set for analyses of immunogenicity in Cohort A or Cohort B for influenza unless otherwise specified. Participants will be analyzed according to the treatment arm to which they were randomized.

The Per Protocol Immunogenicity Set for MN assay consists of a subset of participants randomly sampled from the Full Analysis Set to be tested for MN, who comply with the timing of immunogenicity blood sampling collections to have both Baseline (see section 6.1) and Day 29 assessments using a window of -7 to +14 days, have no major dosing error, have negative RT-PCR test for influenza and SARS-CoV-2 on Day 1, and have no major protocol deviations or conditions/medications that affect the immune response.

The major dosing error ranges, available in Table 2, will be used to determine participant exclusion from the PPIS for MN assay analysis populations.

**Table 2 Exclusion Condition for Dosing Errors** 

Substudies	Arm Titles	Exclusion Conditions
Cohort A (≥65 years of age)	mRNA 1083 + Placebo	Any of the following received: $mRNA-1083 \leq 30~\mu g~OR$ $mRNA-1083 > 60~\mu g~OR$ Fluarix OR Fluzone HD OR Spikevax
	Fluzone HD + Spikevax	Any of the following received: Fluzone HD ≤180 μg OR Spikevax ≤37.5 μg OR mRNA-1083 OR Fluarix
Cohort B (50 to <65 years of age)	mRNA 1083 + Placebo	Any of the following received: $mRNA-1083 \leq 30~\mu g~OR$ $mRNA-1083 > 60~\mu g~OR$ Fluarix OR Fluzone HD OR Spikevax
	Fluarix + Spikevax	Any of the following received: Fluarix ≤45 μg OR Spikevax ≤37.5 μg OR mRNA-1083 OR Fluzone HD

## 5.6 Safety Set

The Safety Set consists of all participants who are randomly assigned and receive the study intervention. The Safety Set will be used for all analyses of safety, except for the solicited ARs. Participants will be included in the treatment arm corresponding to what they actually received according to the as treated scheme given below in Table 3.

**Table 3 Inclusion Conditions for Safety Set** 

Substudies	Arm Titles	Inclusion Conditions
Cohort A	mRNA 1083 + Placebo	Any mRNA 1083 dose
(≥65 years of age)	Fluzone HD + Spikevax	Any Fluzone HD dose OR Any Fluarix dose OR Any Spikevax dose
Cohort B	mRNA 1083 + Placebo	Any mRNA 1083 dose
(50 to <65 years of age)	Fluarix + Spikevax	Any Fluarix dose OR Any Fluzone HD dose OR Any Spikevax dose

## 5.7 Solicited Safety Set

The Solicited Safety Set consists of all participants in the Safety Set who contribute any solicited AR data. The Solicited Safety Set will be used for the analyses of solicited ARs, and participants will be included in the treatment arm corresponding to what they actually received.

#### 6 STATISTICAL ANALYSIS

#### 6.1 General Considerations

All analyses will be conducted using SAS Version 9.4 or higher. Statistical outputs (tables, figures, listings, and datasets) will refer study participants as participants and will use injection of IP and injection interchangeably.

Continuous variables will be summarized using the following descriptive summary statistics: the number of participants (n), mean, standard deviation (SD), median, Q1 and Q3 (only for summaries specified below), as well as minimum (min), and maximum (max). For the summary statistics of all numerical variables unless otherwise specified, the display precision will follow programming standards. Please refer to Appendix B.

Summaries that require Q1 and Q3 for descriptive statistics:

Demographic and baseline characteristics

Study duration

Characteristics of solicited adverse reactions within 7 days after injection

Descriptive summaries of antibody levels

Categorical variables will be summarized using counts and percentages. When count data are presented, the percentage will be suppressed when the count is zero in order to draw attention to the non-zero counts. A row denoted "Missing" will be included in count tabulations where specified on the shells to account for dropouts and missing values. The denominator for all percentages will be the number of participants in the treatment arm within the analysis set of interest, unless otherwise specified.

**Baseline value**, unless specified otherwise, is defined as the most recent non missing measurement (scheduled or unscheduled) collected before the dose/time of IP in this study.

For immunogenicity tests and nasal swab tests, the baseline is defined as the most recent non missing result/measurement (scheduled or unscheduled) collected before or on the date of injection (Day 1). If there are multiple valid results on the same 1st injection date/time or date (if time is not available) the largest value will be considered in the immunogenicity baseline derivation.

The following analysis periods of safety analyses will be used:

**Within 7 days after injection**, this period includes the day of vaccination and 6 subsequent days, or up to the study discontinuation or death, whichever comes earlier. This analysis period will be used for unsolicited and solicited local and systemic AR that occur during this time.

**Up to 28 days after injection**, starts from the day of vaccination (Day 1) and spans 28 days to include the day of vaccination and 27 subsequent days, or up to the study discontinuation or death, whichever comes earlier. This analysis period will be used as the primary analysis period for safety analyses including unsolicited AE, except for solicited AR, unless specified otherwise.

**Throughout the Study**, from the day of vaccination (Day 1) and continues through the earliest date of (study completion, discontinuation from the study, or death).

**Visit window rules**: The analysis visit windows for the immunogenicity protocol-defined visits are provided in Appendix C.

**Unscheduled visit** measurements will be included in the analyses as follows:

In scheduled visit windows per specified visit windowing rules (Appendix C).

In the derivation of baseline/last on-treatment measurements.

In the derivation of maximum/minimum on-treatment values and maximum/minimum change from baseline values for safety analyses.

In individual participant data listings.

**Age**: unless otherwise specified, age is calculated as the age at screening. In the analyses for subgroups defined by age, age at screening will be used for derivation of age groups.

Study day relative to the injection will be calculated as below:

study day prior to the injection will be calculated as: date of assessment/event – date of the injection (resulting in negative study day);

study day on or after the date of the injection will be calculated as: date of assessment/event – date of the injection + 1;

**Duration of an event will** be calculated as (Event end date – Event start date +1). The duration of the study will be calculated for the participants included in the safety set:

Since randomization: date of last visit (as recorded on End of Study [EoS] eCRF) – date of randomization + 1,

Since study injection: date of last visit (as recorded on End of Study [EoS] eCRF) – date of injection + 1.

If the last visit date on the EoS eCRF page is missing, then the latest of either the cut-off date or the last available visit date will be employed. The durations of solicited ARs will be calculated as: reaction end date – reaction start date +1, regardless of whether the AR is intermittent or continued or if the solicited AR continues beyond 7 days.

**Incomplete/missing data**: Imputation rules for missing prior/concomitant medications, non-study vaccinations and procedures are provided in Appendix D. Imputation rules for missing AE dates are provided in Appendix E. Other incomplete/missing data will not be imputed, unless specified otherwise.

